## **9.6 Effectiveness Subgroup Analyses**

The following subgroup analyses for the primary and secondary effectiveness endpoints will be provided:

- Subgroup analysis for primary effectiveness endpoint:

- Response on CSQ-midsection item #1 (overall satisfaction) at 12-week follow-up of final treatment by number of treatment cycles completed
- Response on CSQ-midsection item #1 (overall satisfaction) at 12-week follow-up of final treatment by country
- Subgroup analysis for secondary effectiveness endpoints:
  - Response on CSQ item #1 (CSQ-overall and CSQ for individual treated body area) at 12-week follow-up of final treatment by number of treatment cycles completed
  - Response on CSQ item #1 (CSQ-overall and CSQ for individual treated body area) at 12-week follow-up of final treatment by country
  - Number and proportion of participants with correct identification of baseline vs 12-week post-final treatment images by number of treatment cycles completed
  - Number and proportion of participants with correct identification of baseline vs 12-week post final treatment images by country

- [REDACTED]

## **10.0 Safety Analyses**

### **10.1 General Considerations**

All safety analyses will be conducted in the Safety Population. Baseline is defined as the last non-missing assessment before the first Coolsculpting procedure.

## 10.2 Adverse Events

Adverse events (AEs) will be coded into SOC and PT using the MedDRA. The actual version of the MedDRA will be noted in the statistical tables and clinical study report.

An AE will be considered an adverse device effect (ADE) if the AE has a reasonable possibility (Possible, Probable, or Causal relationship) that the study device caused the event.

An AE will be considered a study procedure related AE if the AE has a reasonable possibility (Possible, Probable, or Causal relationship) that the study procedure caused the event.

If the causal relationship to the study procedure/device is missing, the AE will be considered as related to the study procedure/device. If the severity is missing, the AE will be considered as severe.

### 10.2.1 Treatment-Emergent Adverse Events

An AE (or ADE) will be considered a treatment-emergent adverse event (TEAE) (or treatment-emergent adverse device effect [TEADE]) if the AE (or ADE) began or worsened (increased in severity or became serious) on or after the date (and time, if known) of the first study intervention. An AE (or ADE) will be considered a treatment-emergent serious adverse event (TESAE) (or treatment-emergent serious adverse device effect [TESADE]) if it is a TEAE (or TEADE) that additionally meets any SAE (or SADE) criterion. Product label for CoolSculpting report and risk analysis report will be provided by Abbvie before database lock. Any AE (or ADE) not listed on either document will be considered as an unanticipated AE (or ADE).

TEAEs and TEADEs occurred on or after the date of treatment session 1 and before the date of treatment session 2 are counted for treatment session 1. TEAEs and TEADEs occurred on or after the date of treatment session 2 are counted for treatment session 2.

All AEs and ADEs will be included in data listings. Only TEAEs and TEADEs will be included for summaries, unless stated otherwise. Participants with TEAEs/TEADEs, TEAEs related to study procedure, TESAEs/TESADEs, unanticipated TEAEs/TEADEs (UTEAEs/UTEADEs), unanticipated TESAEs/TESADEs (UTESAEs/UTESADEs), TEAEs leading to discontinuation, and TEAEs leading to death will be summarized.

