**10.5.2. Definition of SAE, SADE, and USADE/UADE**

If an event is not an AE per definition above, then it cannot be an SAE even if serious conditions are met (eg, hospitalization for signs/symptoms of the disease under study, death due to progression of disease).

An SAE is an AE that:
a. Led to death
b. Led to serious deterioration in the health of the participant, that either resulted in:
1. A life-threatening illness or injury. The term 'life-threatening' in the definition of serious refers to an event in which the participant was at risk of death at the time of the event. It does not refer to an event, which hypothetically might have caused death, if it were more severe
2. A permanent impairment of a body structure or a body function
3. Inpatient or prolonged hospitalization, planned hospitalization for a pre-existing condition, or a procedure required by the protocol, without serious deterioration in health, is not considered an SAE
4. Medical or surgical intervention to prevent life-threatening illness or injury or permanent impairment to a body structure or a body function
5. Chronic disease (Medical Device Regulation 2017/745)
c. Led to fetal distress, fetal death, or a congenital abnormality or birth defect
SADE definition

• An SADE is defined as an adverse device effect that has resulted in any of the consequences characteristic of an SAE.

• Any device deficiency that might have led to an SAE if appropriate action had not been taken, intervention had not occurred, or circumstances had been less fortunate.

USADE/UADE definition

• A USADE (also identified as UADE in US Regulations 21 CFR 813.3), defined as a serious adverse device effect which by its nature, incidence, severity, or outcome has not been identified in the current version of the risk analysis report (see Section 2.3).

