### **10.2.2 Adverse Event Overview**

Overall summaries of TEAEs will include:

- The number and percentage of participants reporting at least one TEAE
- The number and percentage of participants reporting at least one TESAE
- The number and percentage of participants reporting at least one UTEAE
- The number and percentage of participants reporting at least one UTESAE
- The number and percentage of participants reporting at least one TEAE related to study procedure
- The number and percentage of participants reporting at least one TESAE related to study procedure
- The number and percentage of participants reporting at least one TEADE
- The number and percentage of participants reporting at least one TESADE
- The number and percentage of participants reporting at least one UTEADE
- The number and percentage of participants reporting at least one UTESADE
- The number and percentage of participants reporting a TEAE leading to study discontinuation
- The number and percentage of participants reporting a TEAE leading to death

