### **10.2.3 Treatment-Emergent Adverse Events by SOC and/or PT**

The number and percentage of participants will be summarized by SOC and PT, with or without by severity, as follows:

- TEAEs by SOC and PT
- TEAEs by SOC, PT, and severity
- Study Procedure Related TEAEs by SOC and PT

- Study Procedure Related TEAEs by SOC, PT and severity
- TEADEs by SOC and PT
- TEADEs by SOC, PT, and severity
- UTEAEs by SOC and PT
- UTESAEs by SOC and PT
- UTEADEs by SOC and PT
- UTESADEs by SOC and PT
- TESAEs by SOC and PT
- TESAEs by SOC, PT and severity
- Study Procedure Related TESAEs by SOC and PT
- Study Procedure Related TESAEs by SOC, PT and severity
- TESADEs by SOC and PT
- TESADEs by SOC, PT, and severity
- TEAEs leading to study discontinuation by SOC and PT
- TEAEs leading to death by SOC and PT

The AE and ADE summary tables will be presented with SOC in alphabetical order and in decreasing frequency within each SOC. If more than 1 AE or ADE is coded to the same PT for the same participant, the participant will be counted only once for that PT using the most severe and most related occurrence for the summarization by severity and by relationship to study intervention.

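### For serious device effects, the SAP's unlisted-event rule is narrower than the protocol's definition of unanticipated, so the UTESADE tables can leave a protocol-defined USADE unflagged

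*SAP*

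**What the plan says.** SAP 10.2.1 names two reference documents: "Product label for CoolSculpting report and risk analysis report will be provided by Abbvie before database lock". The classification rule follows: "Any AE (or ADE) not listed on either document will be considered as an unanticipated AE (or ADE". The SAP does not say how an event is matched to these documents, and it does not refer back to the protocol's definition.

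The same section then names the serious subset, "unanticipated TESAEs/TESADEs (UTESAEs/UTESADEs", without defining it separately. A UTESADE is therefore a treatment-emergent serious adverse device effect that meets the unlisted-event rule. Two outputs depend on it:

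- SAP 10.2.2, the adverse event overview: "The number and percentage of participants reporting at least one UTESADE".
- SAP 10.2.3, the tables by system organ class and preferred term: "UTESADEs by SOC and PT".

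Protocol 10.5.2 defines a USADE (the UADE of the US regulations) as a device effect that meets a seriousness criterion and is one "which by its nature, incidence, severity, or outcome has not been identified in the current version of the risk analysis report". The only reference document there is the risk analysis report; the product label is not mentioned.

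For adverse events in general the protocol is looser. Its safety measures (Synopsis and Section 3) describe unanticipated AEs or SAEs as those not known for the device before. Protocol 9.4.5 plans a summary of unanticipated AEs or ADEs and leaves further safety-analysis detail to the SAP.

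**The concern.** The protocol asks whether a serious device effect was foreseen in each of four respects. The SAP asks only whether it is listed. A serious device effect can be listed and still be unforeseen in how severe it was, how it ended or how often it occurred. The SAP rule would class it as anticipated, and the study report would use the category in a narrower sense than the protocol defines.

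The descriptions in Protocol 2.3.2 and Table 2-2 show why this is a practical question for this device. They attach outcome and frequency to known effects: freeze burn usually heals without lasting harm, late-onset pain clears within weeks, and severe pain is rare. If the risk analysis report carries similar descriptions (an assumption, since it is not among the documents), a serious burn with permanent impairment could meet the protocol definition on outcome alone while counting as listed under the SAP.

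What is at stake is the meaning of the UTESADE row and table. No effectiveness result depends on it.

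**Working it through.** No arithmetic applies. The documents give no event rates and the study tests no hypotheses, so the check compares the two definitions.

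| | Protocol 10.5.2 | SAP 10.2.1 |
|---|---|---|
| Applies to | Serious adverse device effects | Every AE and ADE, and so the UTESADE subset |
| Reference | Risk analysis report, current version | Product label and risk analysis report, no version named |
| Test | Any of nature, incidence, severity or outcome not identified | Not listed on either document |

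Apply both to a serious adverse device effect, reading the SAP test as listed on neither document:

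| Case | Protocol | SAP |
|---|---|---|
| (a) Listed in neither document | Unanticipated | Unanticipated |
| (b) In the risk analysis report, all four attributes as identified there | Anticipated | Anticipated |
| (c) Listed, but severity, outcome or incidence not identified in the risk analysis report | Unanticipated | Anticipated |
| (d) On the label, absent from the risk analysis report | Unanticipated | Anticipated |

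The texts agree in (a) and (b) and disagree in (c) and (d). In both disagreements the SAP leaves a protocol-defined USADE unflagged.

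Case (d) depends on how the SAP sentence is read. If it meant missing from at least one document, (d) would be flagged. Case (c) would still go unflagged for an effect listed in both.

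Next, the other three unanticipated categories. UTEAE, UTESAE and UTEADE are not covered by the four-attribute definition, which is confined to serious device effects. The protocol text nearest to them is the general measure of events not known for the device before, and an unlisted-event rule is a reasonable way to apply that. There is no conflict for these three.

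Last, where a case (c) or (d) event would still appear. It is a TESADE, so it counts in the TESADE row of SAP 10.2.2, in the SAP 10.2.3 TESADE tables with and without severity, and in the listings of all AEs and ADEs. Only the unanticipated flag is absent.

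**The case against.** The strongest reply is that the SAP speaks of an AE or ADE being listed, not of a preferred term. If the label or risk analysis report lists effects with severity attached, matching on the full entry would pick up some differences in severity. Protocol Table 2-2 is built partly in that way: burns are separated by degree, and severe pain has its own entry. This stands as a limit. A reader might infer that none of the 13 event types named there besides the catch-all entry could ever enter the UTESADE table. The documents do not support that, because neither reference document is supplied and the matching rule is not stated. It does not remove the conflict, because the SAP specifies no such matching and names neither incidence nor outcome.

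A reader might also infer that the rule over-counts by calling any unlisted, unrelated illness unanticipated. That is not an error here. The protocol's measure includes unanticipated AEs whatever their cause, and the SAP tabulates UTEAEs and UTEADEs separately.

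A third tempting inference comes from the statement that the reference documents "will be provided by Abbvie before database lock": that a label revised during the study would reclassify events already seen, so the versions should be frozen at first treatment. The documents report no revision, and a freeze would depart from the protocol's reference to the current version. What stands is only that the SAP names no version.

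Finally, event-level safety reporting runs under Protocol 10.5.4 to 10.5.6, not through these tables, and no event disappears from the report. That is correct, and it is why the severity is low.

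**Conclusion.** The concern holds for UTESADE only. SAP 10.2.1 is narrower than Protocol 10.5.2, and followed as written it can class a protocol-defined USADE as anticipated in the overview count and in the table by system organ class and preferred term. The rule is wrong as written, at low severity, because it affects one descriptive flag in a study without hypothesis tests.

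The number of participants affected cannot be computed: the documents give no rates for serious device effects, and the label and risk analysis report are not available. It may be none, since the mismatch shows only if such an event occurs. Case (c) assumes that listing is judged without regard to incidence and outcome, which is the natural reading because the SAP names no such attribute. Case (d) further assumes that the SAP test means listed on neither document.

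**What to change.** In SAP 10.2.1:

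- Define UTESADE by the Protocol 10.5.2 definition, judged against the current version of the risk analysis report, and cite that version in the study report.
- Have the sponsor's medical reviewer classify each TESADE on nature, severity and outcome before database lock.
- Assess incidence by event type, not event by event, because it is a property of the group. Compare it with the rate in the risk analysis report, if there is one; if there is none, say so.
- Keep the unlisted-event rule for UTEAE, UTESAE and UTEADE, and state whether it means absent from both documents or from at least one.

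The cost is a short SAP amendment and a review of what should be few serious device effects. The downside is that a judgement step replaces a purely programmed flag for those events.

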### **10.2.2 Adverse Event Overview**

Overall summaries of TEAEs will include:

- The number and percentage of participants reporting at least one TEAE
- The number and percentage of participants reporting at least one TESAE
- The number and percentage of participants reporting at least one UTEAE
- The number and percentage of participants reporting at least one UTESAE
- The number and percentage of participants reporting at least one TEAE related to study procedure
- The number and percentage of participants reporting at least one TESAE related to study procedure
- The number and percentage of participants reporting at least one TEADE
- The number and percentage of participants reporting at least one TESADE
- The number and percentage of participants reporting at least one UTEADE
- The number and percentage of participants reporting at least one UTESADE
- The number and percentage of participants reporting a TEAE leading to study discontinuation
- The number and percentage of participants reporting a TEAE leading to death

### **10.2.3 Treatment-Emergent Adverse Events by SOC and/or PT**

The number and percentage of participants will be summarized by SOC and PT, with or without by severity, as follows:

- TEAEs by SOC and PT
- TEAEs by SOC, PT, and severity
- Study Procedure Related TEAEs by SOC and PT

- Study Procedure Related TEAEs by SOC, PT and severity
- TEADEs by SOC and PT
- TEADEs by SOC, PT, and severity
- UTEAEs by SOC and PT
- UTESAEs by SOC and PT
- UTEADEs by SOC and PT
- UTESADEs by SOC and PT
- TESAEs by SOC and PT
- TESAEs by SOC, PT and severity
- Study Procedure Related TESAEs by SOC and PT
- Study Procedure Related TESAEs by SOC, PT and severity
- TESADEs by SOC and PT
- TESADEs by SOC, PT, and severity
- TEAEs leading to study discontinuation by SOC and PT
- TEAEs leading to death by SOC and PT

The AE and ADE summary tables will be presented with SOC in alphabetical order and in decreasing frequency within each SOC. If more than 1 AE or ADE is coded to the same PT for the same participant, the participant will be counted only once for that PT using the most severe and most related occurrence for the summarization by severity and by relationship to study intervention.

#### **10.2.4 SAEs (Including Deaths) and Adverse Events Leading to Study Discontinuation**

An SAE is defined as an AE that:

- led to death
- led to serious deterioration in the health of the participant, that either resulted in
  - a life-threatening illness or injury; or
  - a permanent impairment of a body structure or a body function, or
  - in-patient or prolonged hospitalization; or
  - medical or surgical intervention to prevent life-threatening illness or injury or permanent impairment to a body structure or a body function;
  - Chronic disease (EU)
- Led to fetal distress, fetal death, or a congenital abnormality or birth defect

TESAEs, study procedure related TESAEs, TESADEs, TEAEs leading to study discontinuation, and TEAEs leading to death will be summarized in the overall table as in Section 10.2.2, and by SOC and PT as in Section 10.2.3.

#### **10.2.5 Adverse Events of Special Interest**

Not applicable.

#### **10.3 Analysis of Laboratory Data**

Pregnancy test (urine  $\beta$ -HCG) will be performed on Visit 1, Visit 2, and Visit 6. The pregnancy test results will be listed but not summarized.

#### **10.4 Safety Subgroup Analyses**

For TEAEs, the following subgroup analyses will be provided:

- Subgroup analysis by SOC and PT:
  - TEAEs by treated body areas, SOC and PT
- Subgroup analysis by SOC, PT and severity:
  - TEAEs by number of treated body areas, SOC, PT, and severity

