Note: Only body area(s) that were treated at Visit 2 and that require a second treatment session are to be treated at Visit 6. The treatment plan for specific body area(s) may be completed within a 7-day window from when the initial treatment is administered for this visit. The entire treatment session #2 plan for the body area(s) selected for a second treatment must be completed within these 7 days.

- Visit 7 (1-week phone follow-up from last treatment day for participants who received treatment session #2 on any body area)

Note: If any of the following local effects of erythema, bruising, swelling, and/or sensory alteration are reported during this Visit, additional phone follow-up (or in-person visit if aligned to planned study visit) will be scheduled in accordance with the time criteria outlined in Table 2-1 for potential AE categorization.

- Visit 8 (12-week follow-up/exit for participants with any body area that underwent only treatment session 1 at Visit 2, Day 84 + 14 days). If the participant receives only one treatment session to all body areas, this visit is also the study exit visit.

Note: If the participant receives only one treatment session to a specific body area and two treatment sessions to another specific body area, the body area that received only one treatment session will be assessed at this visit. The participant will return at Visit 9 for assessment of body area that received two treatment sessions and study exit.

[figure not shown]
- Visit 9 (20-week follow-up/exit, corresponding to 12-week follow up for participants with any body area that underwent treatment session 2 at Visit 6, Day 140 + 14 days). If the participant receives two treatment sessions to any or all treated body areas, this visit is also the study exit visit.

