Note: Treatment plan may be completed within a 7-day window from the day when the initial treatment is administered for this visit. The entire treatment session #1 plan for all the body areas selected for treatment must be completed within these 7 days.

- Visit 3 (1-week phone follow-up from last treatment day for participants who received treatment session #1 on any body area)

Note: If any of the following local effects of erythema, bruising, swelling, and/or sensory alteration are reported during Visit 3, additional phone follow-up (or in-person visit if aligned to planned study visit) will be scheduled in accordance with the time criteria outlined in Table 2-1 for potential AE categorization.

- Visit 4 (4-week follow-up after treatment session #1, Day 28 + 10 days)
- Visit 5 (8-week follow-up after treatment session #1, Day 56 + 14 days)
- Visit 6 (treatment session #2 [optional], Day 56 + 14 days, can be completed on the same day as Visit 5)

Note: Only body area(s) that were treated at Visit 2 and that require a second treatment session are to be treated at Visit 6. The treatment plan for specific body area(s) may be completed within a 7-day window from when the initial treatment is administered for this visit. The entire treatment session #2 plan for the body area(s) selected for a second treatment must be completed within these 7 days.

- Visit 7 (1-week phone follow-up from last treatment day for participants who received treatment session #2 on any body area)

Note: If any of the following local effects of erythema, bruising, swelling, and/or sensory alteration are reported during this Visit, additional phone follow-up (or in-person visit if aligned to planned study visit) will be scheduled in accordance with the time criteria outlined in Table 2-1 for potential AE categorization.

- Visit 8 (12-week follow-up/exit for participants with any body area that underwent only treatment session 1 at Visit 2, Day 84 + 14 days). If the participant receives only one treatment session to all body areas, this visit is also the study exit visit.

Note: If the participant receives only one treatment session to a specific body area and two treatment sessions to another specific body area, the body area that received only one treatment session will be assessed at this visit. The participant will return at Visit 9 for assessment of body area that received two treatment sessions and study exit.

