#### 4.2. Scientific Rationale for Study Design

There is a need to generate more information regarding the use of CoolSculpting when multiple body areas beyond midsection or torso are included for evaluation. In addition, there is no patient outcome reported data reflecting patient experience when multiple body areas are treated. In addition, this study will evaluate effectiveness by correct identification of baseline vs post-treatment images of the treated body area(s) by at least two out of three blinded, independent reviewers which is consistent with prior CoolSculpting studies for the specified treatment areas. The use of 3D imaging will also provide for evaluation of volumetric changes as a result of treatment. Therefore, there is a need to further evaluate the safety, effectiveness, and patient satisfaction with the CoolSculpting Elite System when cryolipolysis cycles are applied simultaneously or sequentially for noninvasive subcutaneous fat reduction for multiple body areas at an expanded number of clinical sites and across different patient populations.

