### **8.3.1. Time Period and Frequency for Collecting AE and SAE Information**

All AEs/SAEs will be recorded in the AE sections of the eCRF throughout the study periodTable 1-1 as observed or reported spontaneously by study participants.

Medical occurrences that begin before the start of study intervention but after obtaining informed consent will be recorded in the AE section of the eCRF and will be considered pretreatment AEs.

All SAEs will be recorded in the CRF and reported to the sponsor or designee using a SAE form immediately; and under no circumstance should this exceed 24 hours, as indicated in Section 10.5. The investigator will submit any updated SAE data to the sponsor within 24 hours of it being available.

Investigators are not obligated to actively seek all AE or SAE information after conclusion of the study participation. However, if the investigator learns of any SAE, including a death, at any time after a participant has been discharged from the study, and he/she considers the event to be reasonably related to the study intervention or study participation, the investigator must promptly notify the sponsor.

Pandemic infections should be captured as AEs. If the event meets the criteria for an SAE, then follow the SAE reporting directions per the protocol.

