1b If, during this phone follow-up, any of the following local effects of erythema, bruising, swelling, and/or sensory alteration are reported related to treatment session #1, additional phone follow-up (or in-person visit if aligned to planned study visit) will be scheduled in accordance with the time criteria outlined in Table 2-1 for potential AE categorization.

2a Phone follow-up should be scheduled 7 days from last treatment visit day in instance where participant received treatment session #2 over multiple days.

---

- 2b If, during this phone follow-up, any of the following local effects of erythema, bruising, swelling, and/or sensory alteration are reported related to treatment session #2, additional phone follow-up (or in-person visit if aligned to planned study visit) will be scheduled in accordance with the time criteria outlined in Table 2-1 for potential AE categorization.
-  If a participant receives only one treatment session for specific body area(s), the participant will return at Visit 8 for the 12-week post-treatment session #1 follow up assessment and study exit. If a participant receives two treatment sessions to any or all treated body areas, participant will return at Visit 9 for 12-week post-treatment session #2 follow-up and study exit. If a participant receives only one treatment session to one specific body area and two treatment sessions to another specific body area, the participant will return for Visit 8 for 12-week follow-up for the body area that received only one treatment session and Visit 9 for 12-week follow-up of body area that received two treatment sessions. The exit for this participant is Visit 9.
-  For select study sites with 3D camera system, 3D images will also be taken at this time.
-  CSQ-Overall is to be administered only if patient received treatment to midsection (abdomen and flank) plus at least one additional specific body area. The CSQ-Overall should be completed at visit where at least 12-weeks have passed since the final treatment session for all the treated body areas. For example, if the participant receives only one treatment session for one specific body area but two treatment sessions for another specific body area, the CSQ-Overall should be administered at Visit 9 where all the treated body areas will have undergone at least a 12-week post treatment period.

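### The SAP 10.4 table of TEAEs by number of treated body areas uses crude percentages, although follow-up and number of sessions depend on whether any area is retreated; it needs a common-window version and a split by sessions.

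*SAP*

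**What the plan says.** SAP 10.4 lists two subgroup tables for treatment-emergent adverse events (TEAEs). One is by treated body area. The other is "TEAEs by number of treated body areas, SOC, PT, and severity". It names no time window, no split by number of sessions and no exposure measure.

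The statistic comes from SAP 10.2.3: "The number and percentage of participants will be summarized by SOC and PT, with or without by severity, as follows". Repeated events are collapsed, since "the participant will be counted only once for that PT using the most severe and most related occurrence". Each cell is therefore an incidence proportion over whatever time the participant was observed.

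Observation time is set by the exit visit. Protocol 8.3.1 states: "All AEs/SAEs will be recorded in the AE sections of the eCRF throughout the study". Of Visit 8 (Day 84 + 14 days), Protocol 4.1 says: "If the participant receives only one treatment session to all body areas, this visit is also the study exit visit". Of Visit 9 (Day 140 + 14 days), the Protocol synopsis (Overall Design) says: "If the participant receives two treatment sessions to any or all treated body areas, this visit is also the study exit visit". One retreated area is enough to move exit from about Week 12 to about Week 20. SAP 1.0 adds that a second session delayed by the US treatment hold is rescheduled, with the last visit 12 weeks (+14 days) after it, so some participants go beyond Week 20.

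Protocol 6.6 leaves a second session to the investigator, for areas treated at Visit 2. Protocol 5.1 has every participant agree to midsection treatment, and Table 6-1 allows two sessions for every area, midsection included.

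**The concern.** The rule that extends follow-up is "any area retreated". If the decision is made area by area, each added area is another chance to trigger it. The groups in the table could then differ in length of observation and in number of sessions as well as in number of areas.

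The table matters because of the study's rationale. Protocol 4.2 says: "There is a need to generate more information regarding the use of CoolSculpting when multiple body areas beyond midsection or torso are included for evaluation", and goes on to include safety in that need. Of the safety tables listed in the SAP, this is the only one arranged by number of areas. If percentages rise from one area to five, a reader cannot tell whether treating more areas carries more risk, whether those participants were watched for longer, or whether more of them had a second treatment. If percentages are flat, the same ambiguity could hide a real gradient.

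**Working it through.** **Timing.** The documents give no figure for this analysis, but their visit days agree with each other: 84/7 = 12 weeks, 140/7 = 20 weeks, and session 2 at Day 56 plus 84 days = Day 140. The two observation periods differ by a factor of 140/84 = 1.67.

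**Inputs.** From the documents: exit at 12 or 20 weeks, and up to five areas (the rows of Table 6-1, midsection always included). Assumed, because the documents are silent: retreatment probability *pm* for the midsection and *po* for each other area, independent of one another; a 12-week TEAE risk R12 = 10%; and a constant hazard that does not depend on the number of areas *k*. By construction there is no true effect of *k*.

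**Formulas.**
- Chance of the longer follow-up: q = 1 − (1 − pm)(1 − po)^(k−1)
- Mean follow-up in weeks: 12 + 8q
- 20-week risk: R20 = 1 − (1 − R12)^(20/12) = 1 − 0.9^1.667 = 16.1%
- Crude risk in the table: (1 − q)·R12 + q·R20

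**Worked case, pm = po = 0.3.** For k = 1, q = 0.3, follow-up is 12 + 2.4 = 14.4 weeks and risk is 0.7 × 10% + 0.3 × 16.1% = 11.8%. For k = 5, q = 1 − 0.7^5 = 0.832, follow-up is 18.7 weeks and risk is 0.168 × 10% + 0.832 × 16.1% = 15.1%. The ratio is 1.27.

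| pm | po | Weeks, 1 area | Weeks, 5 areas | Risk, 1 area | Risk, 5 areas | Ratio |
|---|---|---|---|---|---|---|
| 0 | 0.5 | 12.0 | 19.5 | 10.0% | 15.7% | 1.57 |
| 0.3 | 0.3 | 14.4 | 18.7 | 11.8% | 15.1% | 1.27 |
| 0.5 | 0.5 | 16.0 | 19.8 | 13.1% | 15.9% | 1.22 |
| 0.8 | 0.5 | 18.4 | 19.9 | 14.9% | 16.0% | 1.08 |
| 0.95 | 0.5 | 19.6 | 20.0 | 15.8% | 16.1% | 1.02 |
| 1 | any | 20.0 | 20.0 | 16.1% | 16.1% | 1.00 |

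The ceiling in this model is R20/R12 = 1.61. At R12 = 30%, R20 is 44.8% and the ceiling is 1.49.

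**Reversal.** Drop the independence assumption and suppose that 80% of midsection-only participants but 50% of multi-area participants have a second session. The risks are 10% + 0.8 × 6.1% = 14.9% and 10% + 0.5 × 6.1% = 13.05%, a ratio of about 0.88.

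**Early hazard.** Suppose 90% of the 12-week cumulative hazard falls in week 1, the rest is spread evenly, and session 2 adds nothing. The 20-week hazard is 0.9 + 0.1 × 19/11 = 1.073 times the 12-week hazard. The 20- against 12-week risk ratio is then only 1.07 (1.06 at R12 = 30%). If instead session 2 restarts the same profile at Week 8, the total is (0.9 + 0.1 × 7/11) + 1 = 1.964 times. The risk is 1 − 0.9^1.964 = 18.7%, a ratio of 1.87, nearly all of it due to the second treatment.

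**Late events.** Table 2-2 of the Protocol says paradoxical adipose hyperplasia may become evident 2 to 5 months after treatment. With onset uniform over that span after session 1 (about Day 61 to Day 152), exit at Day 84 covers (84 − 61)/91 = about 25% and exit at Day 140 covers (140 − 61)/91 = about 87%.

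**Effect of a common window.** Limited to the first 8 weeks, the constant-hazard model gives 1 − 0.9^(8/12) = 6.8% for every k, and the artefact disappears.

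**The case against.** A reader might infer that participants with more areas are in fact watched longer and that the table therefore overstates the harm of treating more areas. The documents do not support this. They give no retreatment rate, and they do not say that areas are retreated independently. Decisions made for one person at one visit may well go together. The midsection is treated in everyone and may itself be retreated, so one-area participants can also stay to Week 20. This objection stands: neither a direction nor a size can be asserted.

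SAP 10.2.1 assigns each TEAE to session 1 or session 2, and table specifications are in a separate document, so a split may be intended. But SAP 10.4 does not invoke that rule, and the rule would not equalise time. Session 1 counts would cover about 84 days for one-session participants and about 56 days for two-session participants, an imbalance in the other direction.

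Protocol 2.3.2 says the risks usually resolve within a few days. That limits the effect of longer observation alone. It does not deal with the new early-risk period after session 2, or with late-onset events.

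The table is descriptive, no hypothesis is tested, and safety by individual area is covered by other tables. That limits the consequences. It does not make this table interpretable for the question it addresses.

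A second session is real added treatment and not only added time. This stands too, and it means that a rate per participant-week would not by itself separate the two.

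**Conclusion.** The point holds in conditional form. As specified, the table cannot separate number of areas from length of follow-up and number of sessions, because both of those depend on whether any area is retreated. The structure is certain from the documents. The size of any distortion is not. Under assumed inputs and a constant hazard, the spurious five-against-one ratio lies between 1.00 and about 1.6. It is close to 1 when most midsections are retreated, and below 1 when midsection-only participants are retreated more often. These ratios describe the assumptions and are not predictions for this study. The primary endpoint is not affected.

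**What to change.** Keep the whole-study table in SAP 10.4 and add:

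- **(a)** the same table restricted to TEAEs with onset from session 1 up to Day 56 or session 2, whichever is first;
- **(b)** the whole-study table shown separately for participants with one session and with two, as SAP 9.1 already does for effectiveness, with mean follow-up and number of sessions reported for each number-of-areas group.

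Events per participant-week should not be the sole remedy.

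The cost is SAP wording and extra table cuts from dates already collected. There are two downsides. The common window closes about when events that appear 2 to 5 months after treatment begin to show, so (a) supplements the whole-study table and does not replace it. The cells in (b) are smaller: five area counts by two session groups is up to 10 cells from about 110 participants, or 11 each if they were evenly spread, which they need not be.
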